1.4 Rationale for allowing 3 different APBI techniques

Prospectively conducted clinical trials have demonstrated the safety and efficacy of each of the APBI techniques that will be allowed on this study. On the recently closed NSABP B-39/RTOG 0413 protocol, A Randomized Phase III study of Conventional Whole Breast Irradiation Versus Partial Breast Irradiation for Women with Stage 0, I, or II Breast Cancer, APBI could be administered with brachytherapy or 3D-CRT at the physician's discretion, highlighting the equipoise that exists between the techniques and justifying pooling outcomes of patients treated with either technique on this study to assess the primary and secondary endpoints. Given the conformal and homogeneous dose distribution of protons as well as the favorable outcomes reported to date, proton APBI will also be allowed at centers where this modality is available. At least one of the three APBI techniques allowed in this study is available at all participating centers. Similar to NSABP-B-39/RTOG 0413, the APBI technique to be utilized will be at the physician's discretion and will be based on technical considerations, availability at the radiation oncology facility, insurance coverage considerations, and patient preference. In addition, after reduction mammoplasty patients will only be allowed if they undergo brachytherapy as the extensive manipulation of breast tissue at the time of surgery is felt to preclude reliable targeting with external beam photon or proton techniques.

2.0 Goals

2.1 Primary:

- 2.11 To evaluate the rate of adverse cosmesis (defined as fair or poor cosmesis) with accelerated 3 fraction APBI at 3 years, compared to baseline.

2.2 Secondary:

- 2.21 To evaluate the acute and late toxicities of accelerated 3 fraction APBI
- 2.22 To evaluate local disease control of accelerated 3 fraction APBI.
- 2.23 To assess the rate of patient reported adverse cosmesis at 2 years, compared to baseline

- 2.23 To assess quality of life and other patient reported outcomes following accelerated 3 fraction APBI
- 2.24 To compare the local control, acute and late toxicities, cosmesis, quality of life and other patient reported outcomes between the three radiation therapy techniques (3D-CRT, proton, brachytherapy).
- 2.24 To evaluate clinical features, dose-volume parameters, and genetic variants associated with fair and poor cosmetic outcome

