16.3 **Secondary Endpoints:** The secondary aims of this study are to characterize acute and late adverse events, assess patient self-reported and panel-reported cosmesis, IBTR rate, and quality of life as well as exploratory comparisons of cosmesis, toxicity, and IBTR rate between the 3 techniques. In addition, regional recurrence rates, distant recurrence rates, invasive disease-free survival, and overall survival will be estimated for each patient group treated with APBI. Blood will be collected for future studies in order to examine molecular and genomic predictors of adverse cosmesis and late toxicity.

The following definitions are used for the secondary endpoints of interest:

- *Acute adverse events* (up to 1 month post-RT): any adverse event, regardless of attribution, that occurs in the first month post-RT.
- *Late adverse events* (up to 3 years post XRT): any adverse event that occurred after the first month post-RT and up to 3 years post-RT.
- *Patient Reported Outcomes/Quality of life:* the Patient-Reported Outcomes Version of the Common Terminology Criteria for Adverse Events (PRO-CTCAE) will be used for patient self-reporting of toxicities in the CTCAE, along with other measures of fatigue, pain, and arm function listed in the appendix.
- *Patient self-reported cosmetic outcomes:* the patient self-reported outcome will be assessed using a modified Harvard Cosmesis Scale in the Breast Cancer Treatment Outcome Scale (BCTOS).
- *Panel assessed cosmetic outcome:* in addition to patient self-reported and physician reported outcomes, cosmesis will be assessed by a panel of breast cancer medical providers using digital photographs. The Panel will be blinded to treatment allocation.
- *IBTR:* this is defined as local recurrence at 3 years from trial registration as a first event. IBTR is defined as both invasive and non-invasive breast cancer involving the same breast parenchyma as the original tumor.
- *Regional recurrence:* invasive breast cancer in the axilla, regional lymph nodes, chest wall, and skin of the ipsilateral breast.
- *Distant recurrence:* metastatic cancer that has either been biopsy confirmed or clinically diagnosed as recurrent invasive breast cancer.

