16.61 *Acute adverse events (up to 90 days post-RT):* All patients who were registered to the study and started treatment will be included in the acute adverse event analysis. An acute adverse event is an AE, regardless of attribution, that occurs up to 90 days post-RT. The maximum grade for each type of acute AE will be recorded for each patient. Data will be summarized as frequencies and relative frequencies. Additionally, the relationship of the adverse event(s) to the study treatment will be taken into consideration.

16.62 *Late adverse events:* All patients who were registered to the study and started treatment will be included in the late adverse event analysis. A late adverse event is an AE, regardless of attribution, that occurs at least 90 days post-RT and up to 3 years post-RT. The maximum grade for each type of late AE will be recorded for each patient. Data will be summarized as frequencies and relative frequencies. Additionally, the relationship of the adverse event(s) to the study treatment will be taken into consideration. Prior APBI reports have suggested rates of grade 3 or 4 toxicity to be $\leq 10\%$.^{18,47,55,56}

16.63 *Quality of life:* The QOL measurements will be summarized at each time point as mean \pm SD and median (minimum value, maximum value). Changes in the QOL measurements from baseline will be determined at each follow-up measurement. These will be displayed as spaghetti plots. The assessment of the changes at each time point will be done with a paired t-test or Wilcoxon signed rank test, whichever is appropriate.

16.64 *Cosmesis*: The values of the cosmesis instruments (patient self-reported and panel-assessed) will be summarized with the frequencies of fair or poor cosmesis events at baseline and 3 years, and the difference at 3 years, as well as their relative exact binomial confidence intervals.

16.65 *IBTR incidence*: The IBTR cumulative incidence will be estimated using a competing risks method (Gooley et al.). The competing risks will be regional/distant breast cancer recurrence and death.

16.66 *Regional recurrence incidence*: The regional breast cancer recurrence cumulative incidence will be estimated using a competing risks method (Gooley et al.). The competing risks will be local/distant breast cancer recurrence and death.

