18.0 Records and Data Collection Procedures

18.1 Submission Timetable

Initial Material(s) -

CRF	Treatment (Compliance with Test Schedule Section 4.0)
Institutional Contacts	
Patient Eligibility	
Demographics	
On-Study	≤2 weeks after registration
Adverse Events- Baseline	
Specimen Submission: Blood (Baseline)	
Specimen Submission: Tissue (Baseline)*	*6 months from accrual
Patient Status: Baseline	
Patient Assessment	
Off Treatment	Submit ≤2 weeks after registration if withdrawal/refusal occurs prior to beginning protocol therapy

Test Schedule Material(s)

CRF	Post Radiation (cycle 2)	Observation ³ (subsequent cycles)
Radiation Treatment Form	X	
Patient Assessment	X	X
Specimen Submission: Blood (post rad tx)	X	

CRF	Post Radiation (cycle 2)	Observation ³ (subsequent cycles)
Adverse Events Solicited	X	X
Adverse Events Other	X ¹	X ¹
Off Treatment: Submit once per patient	X ¹	
Patient Status form	X	X
Adverse Events: Late		X ¹
Specimen Submission: Tissue (Recurrence)		X ¹
Consent Withdrawal form	X ¹	X ¹
Lost to Follow-up	X ¹	X ¹
Breast/Chest Wall Radiotherapy Questionnaire	X	X

1. When applicable
2. Survey will need to be entered manually if has not alternately been scanned or entered electronically
3. Observation (Active monitoring phase): 12 weeks (+/- 4 weeks), 12 months (+/- 30 days), annually for 5 years (+/-3 months). If a patient is still alive 5 years after registration, no further follow-up is required.

Follow-up Material(s)

CRF	Event Monitoring Phase ¹	
	12 months	Annually for 5 years ²
Patient Status: Survival and Disease Status Follow-Up/Event Monitoring	X	X

1. If a patient is still alive 5 years after registration, no further follow-up is required.
2. If patient has a recurrence prior to being off radiation therapy for 5 years, continue to follow yearly.

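### Patient-reported adverse cosmesis is a 2-year goal in section 2.2, but its only planned analysis, in section 16.64, is at 3 years

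*Combined protocol and SAP*

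**What the plan says.** Section 2.2 uses the number 2.23 for two goals. The first is "To assess the rate of patient reported adverse cosmesis at 2 years, compared to baseline"; the second concerns quality of life and other patient-reported outcomes.

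Section 16.3 defines patient self-reported cosmesis by its instrument, a modified Harvard scale within the BCTOS, and gives no assessment time.

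Section 16.64 is the analysis, and it covers both the patient's own rating and the panel's. The summary is specified as "summarized with the frequencies of fair or poor cosmesis events at baseline and 3 years, and the difference at 3 years". Exact binomial intervals are to accompany these figures. It names no other time point.

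On timing, section 18.1 schedules observation visits at 12 weeks, at 12 months and then annually to 5 years. Section 16.44 lets the final analysis begin about 5 years after the trial opens, which it equates with at least 24 months of observation on the last registered patient. Section 16.8 sets the primary endpoint completion date at 3 years of follow-up on the last registered patient.

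**The concern.** A goal and its analysis should name the same quantity. Here the goal is a 2-year change and the analysis yields a 3-year change. Nothing in the documents explains the difference or ranks one time above the other.

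Two things follow. First, carried out as written, the analysis section would not answer the goal as written. Second, because visits are annual, both values are planned to be collected. An author could cite section 2.2 for the 2-year figure or section 16.64 for the 3-year figure, and call either one pre-specified after seeing both. Section 16.8 commits the trial to reporting its secondary endpoints on the public registry, where each outcome should have one unambiguous time point.

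**Working it through.** This is a comparison of texts; the mismatch itself depends on no arithmetic.

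**Step 1: is there a 2-year analysis anywhere?**

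| Section | What it covers | Time point | Gives a 2-year fair/poor rate? |
|---|---|---|---|
| 2.23 (first) | Goal: patient-reported adverse cosmesis, change from baseline | 2 years | States the goal only |
| 16.3 | Endpoint definition | None | No |
| 16.63 | QOL scores | Every follow-up | No |
| 16.64 | Patient and panel fair/poor frequencies and difference | Baseline and 3 years | No |
| 16.7 | Exploratory comparison of the three techniques | None for cosmesis | No |

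Section 16.63 is the nearest candidate, since it says "Changes in the QOL measurements from baseline will be determined at each follow-up measurement". But it summarises scores by mean and median and assesses change by paired t-test or signed rank test. Section 16.3 lists self-reported cosmesis separately from quality of life, and 16.64 gives cosmesis its own analysis. Section 16.63 does not fill the gap.

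**Step 2: is it a data gap or a plan gap?** The annual schedule in 18.1 includes both a 2-year and a 3-year visit, and the test schedule in 4.0 marks cosmetic and QOL assessment during observation. The gap is in the plan. Note 7 to section 4.0 accepts that some assessments may be missed for patients who cannot return, so both values are planned but not guaranteed for every patient.

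**Step 3: is there a planned size for this endpoint?** No. The only sample-size figure belongs to the nurse-rated primary endpoint in 16.41 and 16.42. It reproduces with a 10% rate, a 4-point distance and one-sided 95% confidence:

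n = z² × p(1 − p) / d² = 1.645² × 0.10 × 0.90 / 0.04² = 152.2, rounded up to 153.

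No sample size, significance level or threshold is stated for patient-reported cosmesis at either time, and aligning the time points leaves 153 unchanged.

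**Step 4: would 3-year data be complete at the 24-month trigger?** Patients enrolled in the last 12 months of accrual would not yet have 36 months of follow-up.

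- With the stated accrual of about 3 years, assumed uniform: 12 / 36 = 33% of patients.
- With the monthly rates in 16.44 and a total of 168: 5 × 12 = 60 in year one, then (168 − 60) / 8 = 13.5 months, so 25.5 months in all. The last 12 months enrol 8 × 12 = 96, and 96 / 168 = 57%.
- If the operative condition is instead 5 calendar years, the same rates give the last patient 60 − 25.5 = 34.5 months.

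At the 24-month trigger itself, 2-year follow-up would be essentially complete while 3-year follow-up would not. The trigger therefore has to be settled together with the time point.

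**The case against.** The strongest reply is that the statistical section names a single time, 3 years. That matches the primary endpoint in 2.11, 16.1, 16.2 and 16.5, so the 2 years in the goal is probably a leftover. The endpoint has no test, threshold or decision rule, and the go/no-go rule uses only the nurse-rated endpoint. Section 16.64 already sets patient and panel ratings together at 3 years, so a like-for-like comparison is planned.

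All of this limits the weight of the point, but it does not remove it. The documents do not say that 3 years governs, and the 24-month trigger in 16.44 leaves room for the opposite guess. If 2 years was intended, 16.64 lacks the analysis; if 3 years was intended, the goal is wrong. One of the two sections must change.

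A reader might infer more than the text supports:

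- *That patient rating is the main check on the nurse-rated primary endpoint.* No section gives it that role. Section 16.3 describes the photograph panel as blinded to treatment allocation, while patients in an open-label study know their treatment.
- *That patient results cannot be set beside the 3-year nurse and panel results.* Section 16.64 plans them at 3 years. What lacks a plan is the 2-year summary.

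**Conclusion.** The mismatch stands in the current text: a stated secondary goal has no matching analysis, and either time point could be presented as the pre-specified one. It merits correction, but its weight is limited. The endpoint is secondary and descriptive, and the primary decision is unaffected.

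The documents support no numerical size. A reader might take the 10-point change from 16.42, spread it evenly over 3 years, and infer that a 2-year result understates the effect by 10 − 10 × 2/3 = 3.3 points. That borrows a primary-endpoint assumption and adds a linear time course found nowhere in the documents. The gap would be 0 if all change occurred by 2 years, would approach 10 if it came mainly in year 3, and would reverse in sign if cosmesis improved between the two visits.

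A reader might also infer an inflated type I error, up to 1 − 0.95² = 9.75% for two independent one-sided 5% looks. Section 16.64 summarises and does not test, so the plan has no such error rate to inflate.

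The conclusion assumes only that 16.63 does not cover the fair/poor rate, which follows from how 16.3 and 16.64 separate cosmesis from quality of life.

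**What to change.** 1. Name one main time point for patient-reported adverse cosmesis, in the same terms, in 2.23, 16.3 and 16.64. Three years is the natural choice because it matches the primary endpoint and the panel assessment.
2. Add to 16.64 the 2-year fair/poor rate and its change from baseline, labelled as a descriptive summary. The visit is already in the annual schedule.
3. Reconcile the 24-month final-analysis trigger in 16.44 with the 3-year completion date in 16.8, so that 3-year patient-reported data are complete when analysed.

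The cost is text edits in these sections and one extra descriptive summary. No visit, patient or sample-size change is needed. Editing the goal alone would not be enough, because it would leave a 3-year analysis facing a 24-month trigger.

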3.0 Patient Eligibility

3.1 Inclusion Criteria

- 3.11 Female
- 3.12 Age \geq 50 years at diagnosis
- 3.13 Grade 1-3 invasive ductal, mammary, mucinous, tubular, colloidal, or pure ductal carcinoma in situ (DCIS) measuring \leq 2.5 cm on final pathology (the tumor should be clinical stage T1N0M0 in patients electing brachytherapy in whom the catheter will be placed intraoperatively).
- 3.14 Estrogen Receptor (ER)+ (ER- DCIS meeting other eligibility criteria are eligible)
- 3.15 Unicentric: Patients with microscopic multifocality are eligible as long as the total pathologic tumor size is \leq 2.5cm
- 3.16 Surgical treatment of the breast must have been lumpectomy.
- 3.17 The final margins of the resected specimen must be histologically free of tumor.
- 3.18 Patients with DCIS do not require an axillary staging procedure. For patients with invasive breast cancer (except T1mi), an axillary staging procedure should be performed (either sentinel lymph node biopsy alone or axillary dissection and the axillary node must be pathologically negative) and they should be pathologically node negative.

Note: Patients with N0 (i+) tumors on sentinel lymph node mapping or dissection (i.e., if the tumor deposit is 0.2mm or less as determined by immunohistochemistry or hematoxylin and eosin staining) will also be eligible.

- 3.19 ECOG Performance Status of 0 or 1
- 3.20 Negative pregnancy test done \leq 7 days prior to registration, for women of childbearing potential only.
- 3.21 Ability to complete questionnaire(s) by themselves or with assistance.
- 3.22 Ability to elect radiotherapy care in conjunction with their physician
- 3.23 Able and willing to provide written informed consent

- 3.24 Willingness to return to enrolling institution for follow-up (during the Active Monitoring Phase of the study).
- 3.25 Willing to provide tissue and blood samples for correlative research purposes
- 3.26 Rochester and Arizona patients: Willing to sign consent onto the Mayo Clinic Radiotherapy Patient Outcomes Registry and Biobanking study and collect involved blood specimen prior to the start of radiation therapy, IRB number 15-000136.

3.3 Exclusion Criteria

- 3.31 Any of the following because this study involves therapy that has known genotoxic, mutagenic and teratogenic effects:
 - Pregnant women
 - Nursing women
 - Women of childbearing potential who are unwilling to employ adequate contraception
- 3.32 Neoadjuvant chemotherapy
- 3.33 Prior history of ipsilateral breast cancer
- 3.34 Prior radiation therapy to the ipsilateral breast or thorax
- 3.35 Co-morbid systemic illnesses or other severe concurrent disease which, in the judgment of the investigator, would make the patient inappropriate for entry into this study or interfere significantly with the proper assessment of safety and toxicity of the prescribed regimens.
- 3.36 Active collagen-vascular disease that, in the opinion of the treating physician, would make this protocol unreasonably hazardous for the patient.
- 3.37 Paget's disease of the breast
- 3.38 Proven multicentric carcinoma (DCIS or invasive) in more than one quadrant or separated by 4 or more centimeters or diffuse (>1 quadrant) suspicious calcifications
- 3.39 Histologic evidence of angiolympatic invasion (ALI).
Note: Cases termed focally suspicious for ALI but where no definitive ALI is found are eligible.
- 3.40 Surgical margins that cannot be microscopically assessed or that are positive
- 3.41 Pathologic tumor >2.5cm in size
- 3.42 Metastatic disease
- 3.43 Patients for whom the delivery of APBI is not feasible or any of the dosimetric treatment criteria in section 9.7 have not been met.

3.44 BRCA 1/2 mutation

Note: Patients are not required to undergo BRCA1 and BRCA2 or other genetic mutation tests in order to enroll on the study. However, in the event a patient is tested and is found to be a mutation carrier, she would be excluded from the study.

3.45 Breast implants (patients who have had implants removed are eligible).

3.46 Extensive intraductal component

3.47 Active connective tissue disease

3.48 Reduction mammoplasty if 3DCRT or proton APBI are planned

3.49 Last surgery >10 weeks from enrollment

4.0 Test Schedule

Assessments, tests and procedures	Active Monitoring Phase				Observation
	Baseline ²	Radiation Treatment	Last day of radiation treatment (+/-2 days)	12 weeks (+/- 8 weeks) post-radiation	
History and Physical exam (including breast assessment/exam) ¹	X		X	X	X
Mammogram	X ¹¹				X ⁸
Consent	X				
Cosmetic and QOL Outcome Assessment (see section 11.3 and Appendix)	X		X	X	X
Digital Photograph	X ¹⁰		X	X	X
Histologic Assessment	X ³				
Radiation toxicity assessment (see section 10.4)	X		X	X	X
Serum pregnancy test	X ⁴				
Blood specimen ^{5,R}	X ¹²		X		
Clinically indicated treatment		X			

Surgical tumor specimen ^{6,R}	X ⁹				
----------------------------------------	----------------	--	--	--	--

1. A general clinical history & physical must be done \leq 8 weeks prior to registration. This should include assessment of ECOG performance status (see Appendix I).
2. Procedures done prior to radiation therapy.
3. Outside pathology must be reviewed at the treating institution.
4. For women of childbearing potential only
5. See section 14 for collection time and preparation of samples
6. See section 17 for collection time and preparation of samples
7. Patients that cannot come back to Mayo Rochester within the time constraints of the follow-up schedule; efforts to obtain outside records and send QOL's to be completed will occur however the specifics of the test schedule may not be captured. Observation will occur for a total of 5 years unless the patient goes off study.
8. As clinically indicated
9. Collect post-surgery
10. Ideally prior to surgery but can be done prior to radiation
11. Completed \leq 6 months prior to study entry
12. Radiation Oncology Registry and Biobank (IRB: 15-000136): Blood specimen is required to be collected prior to the start of radiation therapy.
- R. Research required testing

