8.2 Radiation Therapy Adverse Events

The descriptions and grading scales found in the revised NCI Common Terminology Criteria for Adverse Events (CTCAE), version 4 will be utilized for grading all adverse events. All appropriate treatment areas should have access to a copy of the CTCAE, v. 4. A copy of the CTCAE, v. 4 can be downloaded from the CTEP web site
 (██████████).

EVENTS EXPECTED

Erythema, dry desquamation, hyper or hypopigmentation are anticipated to occur commonly. Some patients may develop moist desquamation, which usually heals within 2-3 weeks. Mild swelling of the breast or mild breast pain are also likely side effects of treatment. It is not anticipated that treatment breaks should be needed, as severe acute toxicities are extremely rare.

Transient, persistent, and occasionally symptomatic seroma formation can occur and will be monitored for during treatment and at follow-up. Telangiectasia, and chronic changes in pigmentation can also commonly be seen, as can soft tissue fibrosis.

Infection is less likely, occurring in less than 10% of patients, generally following brachytherapy.

Skin or subcutaneous toxicity requiring surgery, pneumonitis, rib fractures, or any grade 3 or greater complications including pain are uncommon after ABPI, and are expected to occur in <10% of patients

Patients will also undergo venipuncture as part of the study. Risks of that procedure include hematoma, swelling, tenderness and inflammation at the site, persistent bleeding, vasovagal response, and rarely thrombosis and infection.

Method of detection, signs and symptoms, and method of treatment will be reported for all detected toxicities

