16.9 Data & Safety Monitoring

16.91 The principal investigator(s) and the study statistician will review the study at least every quarter to identify accrual, adverse events, and any endpoint problems that might be developing. The Mayo Clinic Cancer Center (MCCC) Data Safety Monitoring Board (DSMB) is responsible for reviewing accrual and safety data for this trial at least twice a year, based on reports provided by the MCCC Statistical Office.

16.92 Adverse Event Stopping Rules: The stopping rules specified below are based on knowledge available at study development. We note that the Adverse Event Stopping Rule may be adjusted in the event of either (1) the study re-opening to accrual or (2) at any time during the conduct of the trial and in consideration of newly acquired information regarding the adverse event profile of the treatment(s) under investigation. The study team may choose to suspend accrual because of unexpected adverse event profiles that have not crossed the specified rule below. The following rule will be evaluated for each arm separately.

Accrual will be temporarily suspended if at any time we observe events considered at least possibly related to study treatment (i.e. an adverse event with attribute specified as “possible,” “probable,” or “definite”) that satisfy one of the following:

- If 3 or more patients in the first 15 treated patients experience a grade 3 or higher adverse event, besides acute dermatitis, that is at least possibly related to treatment within 90 days post treatment..
- After the first 15 patients have been treated: if $\geq 20\%$ of all patients experience a grade 3 or higher adverse event, besides acute dermatitis, that is at least possibly related to treatment within 90 days post treatment.

Similarly, within each of the modalities (photon, proton, or brachytherapy APBI), accrual will be suspended for that modality:

- If 6 or more patients in the first 30 treated patients experience a grade 3 or higher adverse event at least possibly related to treatment at any time after 6 months following completion of the protocol treatment.
- After the first 30 patients have been treated: if $\geq 20\%$ of all patients experience a grade 3 or higher adverse event at least possibly related to

treatment at any time after 6 months following the completion of protocol treatment.

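### The one scheduled toxicity assessment between the end of radiation and 12 months has two contradictory windows, and both close after the 90-day limit of the acute endpoint and the early suspension rule

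*Combined protocol and SAP*

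**What the plan says.** The test schedule in 4.0 has a radiation toxicity assessment at baseline, at "Last day of radiation treatment (+/-2 days"), at "12 weeks (+/- 8 weeks) post-radiation", and then in the observation column. Footnote 3 of the submission timetable in 18.1 describes the same follow-up as "12 weeks (+/- 4 weeks), 12 months (+/- 30 days), annually for 5 years (+/-3 months"). Section 10.4 lists the toxicities to be graded at baseline and at each evaluation.

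Three places set time limits on what is graded:

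- Section 16.61: "An acute adverse event is an AE, regardless of attribution, that occurs up to 90 days post-RT". It asks for the maximum grade of each type of acute event per patient. Section 16.62 starts late events at "at least 90 days post-RT and up to 3 years post-RT".
- Section 16.3 defines an acute event differently, as "any adverse event, regardless of attribution, that occurs in the first month post-RT", with late events starting after that month.
- Section 16.92 suspends accrual on early events: "If 3 or more patients in the first 15 treated patients experience a grade 3 or higher adverse event, besides acute dermatitis", at least possibly related and within 90 days of treatment. After the first 15 patients the threshold becomes 20% of all patients, with the same 90-day limit. The rule is evaluated for each arm separately.

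**The concern.** Acute toxicity is a named secondary goal (2.21), and the 90-day suspension rule depends on early grade 3 or higher events becoming known. The schedule provides one graded look after the last treatment day, with two different tolerances. Under either tolerance that look may come after the acute period has ended. A visit on day 35 or day 130 satisfies 4.0 and deviates from 18.1, so sites and data managers have no single standard for a visit that is on time.

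At stake are the completeness of the maximum acute grade that 16.61 calls for, comparability between patients seen at very different times, and how promptly the suspension rule is informed. The primary endpoint, cosmesis at 3 years, is not affected.

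**Working it through.** The plan states no figure to reproduce here. The check converts the windows to days after radiation and compares them with the limits.

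1. **Window in 4.0.** (12 − 8) × 7 = day 28; (12 + 8) × 7 = day 140.
2. **Window in 18.1, footnote 3.** (12 − 4) × 7 = day 56; (12 + 4) × 7 = day 112.
3. **Excess over day 90 (16.61, 16.92).** 140 − 90 = 50 days; 112 − 90 = 22 days. The nominal visit is 12 × 7 = day 84, which leaves 90 − 84 = 6 days.
4. **Neighbouring assessments.** The one before is on the last treatment day ±2 days, so at most day 2. The one after is at 12 months ±30 days (18.1), so at the earliest 365 − 30 = day 335. The 12-week visit is therefore the only scheduled 10.4 grading between about day 2 and day 335. The observation column of 4.0 shows no legible timing, so the later visit rests on 18.1.
5. **Share of each window after day 90.** For ±8 weeks: 50 / (140 − 28) = 50/112 = 0.446. For ±4 weeks: 22 / (112 − 56) = 22/56 = 0.393. These are shares of calendar days. They are shares of visits only if visits are spread evenly, which the documents do not say.
6. **Against the one-month definition in 16.3 (taken as day 30).** The ±8 window overlaps the acute period on days 28 to 30 only, about 2 days. The ±4 window does not overlap it.
7. **Timeliness.** Section 16.44 projects 5, later 8, patients per month. Taking a month as 365/12 = 30.4 days, 50 days is 1.64 months, or about 8 to 13 further patients across techniques (1.64 × 5 = 8.2; 1.64 × 8 = 13.2). This applies to an event that first becomes known at a day-140 visit rather than by day 90.
8. **Illustration for the 3-of-15 rule.** Let p be the true rate of qualifying early events and m the share that never becomes known. The chance of 3 or more is P(X ≥ 3) with X ~ Binomial(15, p(1 − m)). At an assumed p = 20%:

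| m (assumed) | P(3 or more of 15) |
|---|---|
| 0 | 0.602 |
| 20% | 0.439 |
| 39.3% | 0.271 |
| 44.6% | 0.227 |

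The documents give neither p nor m. The last two rows treat every visit after day 90 as a missed event. That is a pessimistic reading, included only to show the range.

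**The case against.** The strongest reply is that a visit after day 90 need not cost an event or its classification. Sections 16.61 and 16.62 classify by when an event occurs, not by when it is graded. Section 10.3 has the worksheet and log completed whenever an event is identified, and its example form records the dates of occurrence and resolution. Section 18.1 also has a form for other adverse events, and the 12-week visit includes a history. All of this stands. A reader might infer that this visit is the only way to capture acute toxicity, or that a reaction graded on day 120 is automatically filed as late. The documents support neither. What remains is that the worksheet is labelled an example, reporting between visits is not scheduled grading of the 10.4 list, and nothing in 10.4 asks for the worst grade since the previous assessment. A grade seen on day 120 cannot be placed in the acute period without an onset date.

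A reader might also point to 8.2, "Some patients may develop moist desquamation, which usually heals within 2-3 weeks", and conclude that such reactions are always gone before the visit. Section 8.2 gives a healing time but no onset time. A reaction that begins and heals within the first three weeks precedes both windows, but one that begins in week 2 could still be present on day 28. Nor does the example show that the suspension rule is weakened, because that rule leaves out acute dermatitis.

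Finally, a visit that closes by day 90 still cannot observe a reaction that has already healed. This is correct: the onset-dated worst grade does that work. Closing the window ensures a graded look inside the 90-day period and makes the information timely.

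**Conclusion.** The point holds as an inconsistency in scheduling and definitions. The two windows contradict each other, both extend past day 90 (by 50 and 22 days), and the acute period itself is defined as one month in 16.3 and 90 days in 16.61. A patient can comply fully and have no scheduled 10.4 grading between about day 2 and day 90, although 16.61 needs a maximum grade over that period. Acute maximum grades may therefore be under-captured, and the 90-day suspension rule may be informed late.

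The size of any under-capture cannot be derived from the documents. The 45% and 39% figures assume an even spread of visits and describe visit timing, not missed events. It would go too far to read them as the amount by which acute rates are biased low, since reporting between visits and retrospective dating may recover some or all events. No sample size, power or alpha figure changes. The correction should be made, but it does not threaten the primary analysis.

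**What to change.** 1. Reconcile the acute/late cut-off across 16.3, 16.61 and 16.62, and say on which side day 90 falls if that limit is kept, since 16.61 and 16.62 both include it.
2. State one window for the 12-week visit, in identical terms in 4.0 and in footnote 3 of 18.1. If 90 days is kept, the window should close by day 90, for example one visit between week 4 and day 90 after radiation. If one month is chosen instead, such a visit falls almost wholly in the late period. Acute data would then rest on item 3, and the 90-day limit in 16.92 would still need a graded look by day 90.
3. At that visit, require for each 10.4 item the worst grade since the end of radiation with its onset date, as well as the grade on the day. The existing rule of classifying by occurrence can then be applied.

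The cost is a short amendment, a tighter upper limit on visit scheduling and a small change to an existing form. The actual electronic form is not in the documents, so some of these fields may already exist. No extra visit is needed.
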